5.1. Study Design

*Eligibility period determined between a minimum of 30 days and a maximum of 40 days. Investigators may have up to 5 additional days (beyond the 40 days) if needed to schedule patients' Visit 3 appointment.

Abbreviations: OLE = open-label extension; SP = study period.

Figure CGAI.5.1. Illustration of study design for Clinical Protocol I5Q-MC-CGAI.

5.2. Determination of Sample Size

The study will enroll approximately 1140 patients. Eligible patients will be randomized in blinded fashion in a 2:1:1 ratio to placebo (approximately 570 patients), LY2951742 120 mg/month (approximately 285 patients), or 240 mg/month (approximately 285 patients). With the assumption of a 15% discontinuation rate and an effect size of 0.30 in the last month of the 3-month treatment phase, it is estimated that this sample size will provide approximately 95% power that at least 1 dose of LY2951742 will separate from placebo at a 1-sided 0.025 significance level based on simulations using Dunnett test. Assumptions were based on data from 2 double-blind, placebo-controlled, Phase 2 studies, with adjustment to reflect greater variability expected in a larger, multi-country Phase 3 study.

5.3. Randomization and Treatment Assignment

Patients will be randomized in a 2:1:1 ratio to placebo, LY2951742 120 mg/month, or 240 mg/month. Randomization will be stratified within country and by acute headache medication overuse (yes versus no), and use of concurrent migraine prophylactic medication (yes versus no).

^a Patients randomized to the 120 mg dose will receive a loading dose of 240 mg at the first injection only (Visit 3).

^b At Visit 7, all patients who enter the open-label extension will receive LY2951742 at a dose of 240 mg.

^c At Visit 8, all patients will receive LY2951742 at a dose of 120 mg.

d Starting at Visit 9, patients will have the option to receive either LY2951742 dose of 120 mg or 240 mg (flexible dosing).

The acute headache medication overuse will be based on the frequency of acute headache medication intake during the 30-day baseline, and will be adapted from Section 8.2 of the ICHD-3 beta guidelines (ICHD-3 2013).

To ensure an appropriate balance of patients with concurrent prophylaxis use, the sponsor will stop enrollment of patients with concurrent prophylaxis use if the number of patients exceeds approximately 1/3.

5.4. Endpoints

5.4.1. Efficacy Endpoints

Migraine and headache endpoints are defined in Table CGAI.5.1. Each month is defined as a 30-day period with migraine or headache measures normalized from the visit intervals.

 Table CGAI.5.1.
 Migraine and Headache Endpoint Definitions

Diagnosis	Definition/Criteria		
Migraine headache	A headache, with or without aura, of ≥30 minutes duration with both of the		
	following required features (A and B):		
	A. At least 2 of the following headache characteristics:		
	Unilateral location		
	Pulsatile quality		
	Moderate or severe pain intensity		
	Aggravation by or causing avoidance of routine physical activity		
	AND		
	B. During headache at least 1 of the following:		
	Nausea and/or vomiting		
	Photophobia and phonophobia		
	OR		
	C. The headache is believed by the patient to be migraine at onset and is		
	relieved by a triptan or ergot derivative.		
	(Definition adapted from the Standard International Headache Society [IHS] International Classification of Headache Disorders (ICHD)-3 beta)		
Probable migraine	A headache of ≥30 minutes, but missing 1 of the migraine features in the IHS ICHD-3 beta definition. To be exact, it meets either at least 2 A criteria and 0 B criteria, or 1 A criteria and at least 1 B criteria. It must not meet criterion C.		
Migraine headache day	A calendar day on which a migraine headache or probable migraine		
(primary objective)	headache occurs.		
ICHD migraine headache	A calendar day on which a migraine occurs.		
day			
Migraine headache attack	Beginning on any day a migraine headache is recorded and ends when a		
	migraine-free day occurs.		
Non-migraine headache	All headaches of ≥30 minutes duration not fulfilling the definition of		
	migraine or probable migraine.		
Non-migraine headache day	A calendar day on which a non-migraine headache occurs.		
Headache day	A calendar day on which any type of headache occurs (including migraine,		
	probable migraine, and non-migraine headache).		

Headache information will be collected via an electronic patient-reported outcomes (ePRO) diary. Patients will need to enter ePRO diary data daily beginning from Visit 2, continuing until Visit 18.

Information recorded in the ePRO diary, the possible responses and the assignment to the type of headache is presented in Table CGAI.5.2.

Table CGAI.5.2. ePRO Diary Questions, Responses, and Assignment to Headache Type

QUESTION	RESPONSES	HEADACHE ASSIGNMENT	
Q1. Yesterday, did you have a headache that lasted for thirty minutes or more?	Yes	Migraine if at least 2 migraine Criteria As and at least 1 migraine Criterion B are met; or Migraine Criterion C is met.	
	No ^a		
Q2. Enter the total number of hours you had a headache yesterday.	Range 1 to 24	If ≥ 1 the headache will be counted as a headache day.	
Q3. Yesterday, what was the worst headache	Mild		
pain?	Moderate	Migraine Criteria A	
	Severe	Migraine Criteria A	
Q4. Yesterday, was the headache throbbing or	Yes	Migraine Criteria A	
pounding?	No		
Q5. Yesterday, was the headache just on the	Yes	Migraine Criteria A	
right or left side of your head?	No		
Q6. Yesterday, was the headache made worse	Yes	Migraine Criteria A	
by your usual daily activity?	No		
Q7. Yesterday, did the headache come with	Yes	Migraine Criteria B	
sensitivity to light and sound?	No		
Q8. Yesterday, did you feel sick to the	Yes	Migraine Criteria B	
stomach or throw-up with the headache?	No		
Q9. Yesterday, did you have your menstrual	Yes		
period (if female)?	No		
Q10. Yesterday, did you take any medicine	Yes	Medication will only count as headache	
for your headache?		medication on a day a headache occurred.	
	No		
Q11. Yesterday, did you take any medicine	Yes		
for pain other than headache?	No		
Q12. Yesterday, did you experience aura?	Yes		
	No		
Q13. Yesterday, did you experience any	Yes		
warning symptoms (prodrome	No		
symptoms) that a migraine was coming			
other than aura?			
Q14. Yesterday, do you believe you	Yes	Migraine Criterion C	
experienced a migraine AND it was relieved by a triptan or ergot derivative?	No		

^a If "No" is answered for Q1, then the patients will skip Q2 - Q6, and Q14, only answer questions Q7 - Q13 by removing reference to headache.

Primary Measure: Migraine Headache Days

The primary measure is the number of monthly migraine headache days (per 30-day period). A migraine headache day is defined as a calendar day on which a **migraine or probable migraine** occurs.

The primary measure of the number of monthly migraine headache days in each 30-day period will be summarized from daily data for each patient in that period (including approximately 30 days of daily data from the baseline period prior to randomization, 3 months of daily data during double-blind treatment phase, 9 months of daily data during open-label treatment phase, and 4 months of daily data during post-treatment phase).

The daily data will reflect whether the patients meet the migraine / probable migraine criteria; those data will be aggregated, and the number of migraine headache days will be provided for each of the 30-day periods. In calculating the number of migraine headache days for each period, if the period is not equal to 30 days, the number of migraine headache days will be adjusted by multiplying the number of migraine headache days by (30/x) where 'x' is the total number of non-missing diary days in the period.

For the 4 months of post-treatment period, the monthly intervals will be derived as below:

- Firstly, the 2-month visit interval will be split into two 1-month periods for efficacy measures. If the number of days between 2 visits (visit x+1 date visit x date + 1) is even, the first half will be in the first 1-month period and the second half will be in the second 1-month period. If the number of days between 2 visits is odd, then the days will be split similarly, but the first 1-month period will have 1 day more than the second 1-month period.
- Secondly, after the 2-month visit intervals are split into two 1-month periods, the monthly data will be derived in the same way for each 1-month period as for treatment phase. For patients who discontinued early during post-treatment phase (Study Period V [SP V]), if the date of discontinuation is within 30 days of the previous visit date, all data between the previous visit date and the discontinuation date will go to 1 monthly period; if the date of discontinuation is more than 30 days of the previous visit date, then the first 30 days will be the first monthly period, and the rest will be considered as part of the second monthly period.

This approach to missing ePRO diary data assumed that the rate of migraine headache per day is the same for days with missing and nonmissing ePRO diary days. The same approach will also be applied to secondary and exploratory efficacy measures that are derived from ePRO data.

Additionally, if the compliance rate for a monthly interval is \leq 50%, then all endpoints to be derived from the ePRO diary data for that 1-month period will be considered missing.

For the post-treatment phase, the derived 1-month periods (resulting from splitting the 2-month visit interval) will be treated similarly.

For a patient who discontinues early in the double-blind (Study Period III [SP III]) or open-label treatment phase (Study Period IV [SP IV]) or post-treatment phase (SP V), compliance rate for the last month of that study period will be calculated with a denominator of 30 days (or the actual number of days in the interval if greater than 30).

For the rest of months and patients, the compliance rate will be calculated as described in Section 5.5.7.

Other Secondary and Exploratory Efficacy Measures

The same approach for adjusting the number of days within each period to a 30-day period and the same approach to imputing monthly data based on compliance as for the primary measure will be applied to all efficacy measures that are derived from ePRO diary data and need normalization to 30-day period, including:

- Number of ICHD migraine headache days is calculated as the number of calendar days in a 30-day period on which a migraine occurs. Probable migraine is excluded.
- **Number of headache days** is calculated as the number of calendar days in a 30-day period on which a headache occurs.
- Number of moderate-severe headache days is calculated as the number of calendar days in a 30-day period on which a headache occurs with a moderate or severe severity.
- **Number of headache hours** is calculated as the total number of headache hours in a 30-day period on which a headache occurred.
- **Number of migraine headache hours** is calculated as the total number of headache hours in a 30-day period on days when a migraine or probable migraine occurs.
- Number of migraine headache days with medication use is calculated as the number of calendar days in a 30-day period on which migraine or probable migraine occurs and abortive medication is used.
- Number of migraine attacks is calculated as the number of sets of consecutive migraine headache days separated by at least 1 migraine headache-free day in a 30-day period. For example, a migraine headache day starting on 5JAN and ending on 6JAN will result in a migraine headache free day on 7JAN (assuming that it is not a migraine headache day on 7JAN). This will count as 1 migraine attack that started on 5JAN and ended on 6JAN. For migraine attack that begins in 1 30-day period but ends in another, only 1 migraine attack will be counted in the first of the 2 periods. For example, in the case of 7 days of consecutive migraine headache days with 3 days in baseline period and 4 days in Month 1, only 1 migraine attack will be counted in the baseline period; the 4 days of migraine headache days in Month 1 will not be counted as migraine attack in Month 1.

Additional secondary and exploratory efficacy measures will be derived as follows:

• Mean severity of remaining migraine headaches will be calculated at each period (including baseline and any postbaseline periods). For the calculation of mean severity, for days with migraine or probable migraine, severity varies from 1 to 3 with 1=mild, 2=moderate, and 3=severe. The mean severity for each period will be calculated as:

Sum of Severity of migraine headache days in the period # of migraine headache days in the Period

For periods with zero migraine headache days, the mean severity is considered not applicable hence missing in the analysis data set.

• **Proportion of migraine headache days requiring medication use** for treatment of migraine or probable migraine headache will be calculated at each period as:

number of migraine headache days with medication use number of migraine headache days in the Period

For periods with 0 migraine headache days, the proportion would be missing.

• Percent change from baseline in the number of migraine headache days will be calculated for any postbaseline 30-day period as:

$$-1*\frac{100 \times (\text{\# of MHD in Month Y} - \text{\# of MHD in baseline period})}{\text{\# of MHD in baseline period}}$$

- An X% responder is defined as Yes, if any patient who has a ≥X% reduction in the total number of migraine headache days in a 30-day period relative to baseline period, as No if otherwise. Therefore, if the percent change from baseline in the number of migraine headache days is ≥X%, the patient will be counted as an X% responder. In other words, if the response rate defined above in a month is ≥X%, then the patient will be an X% responder in that month. Indicators of X% responders will be derived for X (X=0, 5, 10, ..., 95, and 100).
- 50% responders sustained for all 3 months during double-blind treatment phase in the number of migraine headache days is defined as meeting 50% responder criterion in migraine headache days for Month 1 to Month 3 in the double-blind treatment phase.
- Proportion of patients who continue to demonstrate 50% response for at least 6 (not necessarily consecutive) of the 9 months in the open-label treatment period. This analysis will include patients previously treated with LY2951742 who met 50% response criteria at Month 3 in the double-blind treatment phase (SP III) and entered the open-label treatment phase (SP IV). If a patient discontinued early during SP IV and met 50% response for 6 months, the patient will be defined as a responder, any patient who discontinued before Month 6 of the open-label phase will be counted as a non-responder.

- **Time to first 50% response (in months)** is defined as the first month when 50% response is met. If a patient has not met 50% response during SP III, the patient will be censored at the last month where 50% response status is not missing.
- Time to first loss of 50% response in post-treatment phase (in months) is defined as the time from the beginning of the post-treatment phase to the first month when 50% response is no longer met during the post-treatment phase (SP V). If a patient has met 50% response during all the months of SP V, the patient will be censored at the last month where 50% response status is not missing. This analysis will be conducted only for patients who met 50% response criteria at their last injection interval and are also entered into SP V.
- Time to initiation of treatment with a migraine preventive medication (in days) in the post-treatment phase is defined as the disposition date of the previous study period before entering SP V minus the date of start of the migraine preventive medication (based on information collected from concomitant medication e lectronic case report form [eCRF]) in the post-treatment phase. If a patient did not initiate preventive treatment during SP V, they will be censored at the disposition date of SP V. This analysis will be conducted only for patients who entered SP V and those who are not in concurrent preventive treatment group.
- Number of migraine headache days with nausea and/or vomiting is calculated as the total number of migraine headache days with an answer of "yes" to Question 8 in a 30-day period.
- Number of migraine headache days with photophobia and phonophobia is calculated as the total number of migraine headache days with an answer of "yes" to Question 7 in a 30-day period.
- Number of migraine headache days with aura is calculated as the total number of migraine headache days with an answer of "yes" to Question 12 in a 30-day period.
- Number of migraine headache days with prodrome symptoms other than aura is calculated as the total number of migraine headache days with an answer of "yes" to Question 13 in a 30-day period.
- Number of non-migraine headache days with aura is calculated as the total number of non-migraine headache days with an answer of "yes" to Question 12 in a 30-day period.
- **Proportion of aura among migraine attacks** is calculated as follows: 1) among all the migraine attacks, only if aura happened on the first day of migraine attack, it will be counted as migraine attack with aura, 2) then within each period, proportion of aura among migraine attacks is calculated as the total number of migraine attacks with aura divided by total number of migraine attacks.
- Number of days with abortive medication use is calculated as the number of calendar days in a 30-day period on which abortive medication is used.
- Number of classes of abortive medications used is calculated as the total number of classes of abortive medications taken during a 30-day period.

Abortive medication use will be classified into the following 5 classes: triptans, nonsteroidal anti-inflammatory drugs (NSAIDs)/aspirin, acetaminophen/paracetamol, ergots, anti-nausea. If Question 10 in patient diary questionnaire has an answer of "No", any abortive medication entered for that date will not be included in the analyses.

- Number of classes of abortive medications used on migraine headache days is calculated as the total number of classes of abortive medications taken on migraine headache days during a 30-day period.
- Average number of classes of abortive medications used per day is calculated as follows for each period:

$$\frac{\sum_{i=1}^5 i*n_i}{\sum_{i=0}^5 n_i}$$

Where n_i denotes the number of days during a period with i class(es) of abortive medication use, and i = 0,1,...,5.

• Average number of classes of abortive medications used per migraine headache day is calculated as follows for each period:

$$\frac{\sum_{i=1}^{5} i * m_i}{\sum_{i=0}^{5} m_i}$$

Where m_i denotes the number of migraine headache days during a period with i class(es) of abortive medication use, and i = 0,1,...,5.

- **Number of days with triptan use** is calculated as the number of days with triptan use during a 30-day period.
- Number of migraine headache days with triptan use is calculated as the number of migraine headache days with triptan use during a 30-day period.
- Number of days with NSAIDs/aspirin use is calculated as the number of calendar days with NSAIDs/aspirin use during a 30-day period.
- Number of migraine headache days with NSAIDs/aspirin use is calculated as the number of migraine headache days with NSAIDs/aspirin use during a 30-day period.
- Number of days with acetaminophen/paracetamol use is calculated as the number of days with acetaminophen/paracetamol use during a 30-day period.
- Number of migraine headache days with acetaminophen/paracetamol use is calculated as the number of migraine headache days with acetaminophen/paracetamol use during a 30-day period.
- **Number of days with ergot use** is calculated as the number of days with ergot use during a 30-day period.
- Number of migraine headache days with ergot use is calculated as the number of migraine headache days with ergot use during a 30-day period.

- Number of days with anti-nausea medication use is calculated as the number of days with anti-nausea medication use during a 30-day period.
- Number of migraine headache days with anti-nausea medication use is calculated as the number of migraine headache days with anti-nausea medication use during a 30-day period.
- Number of days with multiple class medication use is calculated as the number of
 days with multiple class medication use during a 30-day period.
 Multiple class medication use is defined as using at least 2 of the 5 classes (defined
 above) on a day.
- Number of migraine headache days with multiple class medication use is calculated as the number of migraine headache days with multiple class medication use during a 30-day period.
- Number of weekly migraine headache days in Month 1 is calculated as the number of migraine headache days in a 7-day period on which a migraine headache occurs. At month 1, the first 7 calendar days will be counted as week 1, the second 7 calendar days will be counted as week 2, the third 7 calendar days will be counted as week 3, and the rest of days will be counted as week 4.

Combination medications (such as aspirin/acetaminophen/caffeine) will be counted in each medication category that applies (such as NSAIDs/aspirin and Acetaminophen/paracetamol).

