To assess the robustness of the MMRM results to deviations from normality assumption, a sensitivity analysis for raw number of migraine headache days (total number of migraine headache days for each interval without normalization to 30-day period) will be conducted with a repeated measures negative binomial regression model fitted with SAS PROC GLIMMIX. The model will include treatment, pooled country, month, baseline medication overuse (yes versus no), concurrent prophylaxis use (yes versus no) and treatment-by-month interaction, as well as the continuous fixed covariates of baseline number of monthly migraine headache days and baseline-by-month interaction, log (number of compliant days within each month/30) as the offset in the model. In case of non-convergence, pooled country and/or baseline-by-month interaction may be excluded from the model. Directional consistency of treatment effects from this model and the primary analysis MMRM model as specified in Section 5.5.10.1 will be examined.

In addition, as another form of sensitivity analysis, residuals from the primary analysis MMRM model will be examined and outliers identified. Consistency of results before and after removing patients with outlier residuals will be examined.

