Appendix Table 1. Description of Important Protocol Deviations

Category	Subcategory	Study-specific	Source	Methods of Identification
Informed Consent	ICF not obtained	Initial ICF date is missing or is after (Visit 1 date or Visit 1 lab date)	Programmable - Stats	For all patients, if initial ICF date is missing or after (Visit 1 date or Visit 1 lab date).
Form (ICF)	Improper ICF	ICF not signed prior to initiation of protocol procedures	Non-programmable - Monitor identified	Or determined by study team
		Age <18 or >65 years old at study entry	Non-programmable- Monitor identified	
		BMI ≥40 at baseline	Programmable - Stats	
		Do not meet criteria of at least 15 normalized headache days of which 8 must have features of migraine	Programmable - Stats	Number of normalized headache days <15, or number of normalized migraine headache days < 8
	leal along	At least one headache free day	Programmable - Stats	Number of normalized headache days > 29
Eligibility	Inclusion/ Exclusion	Baseline ePRO compliance <80%	Programmable - Stats	
		Female patients who have a positive serum pregnancy test prior to randomization visit	Programmable - Stats	For randomized female patients, if serum pregnancy test is positive any time prior to Visit 3
		Female patients who have a positive or no serum pregnancy test prior to randomization visit	Non-programmable- Monitor identified	
		Insufficient washout of prohibited migraine preventive medication for at least 30 days prior to Visit 2	Programmable - Stats	Patients must have discontinued such treatment at least 30 days prior to Visit 2.

Category	Subcategory	Study-specific	Source	Methods of Identification
		Insufficient washout of Botulinum toxin A and B at least 4 months prior to Visit 2	Non-programmable- Study team identified	Stats will create the list of patients meet this IPD criteria. Among those, the true IPDs will be manually added into non-programmable excel sheet
		With suicidal ideation (Q4 or Q5) within past month of visit 1.	Programmable - Stats	Randomized patients with answer "yes" for C-SSRS suicidal ideation Q4 or Q5 occurred within past 1 month of visit 1.
		Positive or no urine drug screen prior to randomization	Programmable - Stats	For randomized patients if prior to visit 3, a patient has a positive UDS result and a repeated UDS not done or last repeat UDS is positive or UDS never collected.

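### SAP 5.4.1 ties the missing-diary scaling to period length, so as written, missed days in an exactly 30-day period are scored as migraine-free

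*SAP*

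**What the plan says.** SAP 5.4.1 builds the monthly number of migraine headache days from daily diary data. Its operative rule is conditional: "if the period is not equal to 30 days, the number of migraine headache days will be adjusted by multiplying" by 30/x, with x the number of days in the period that have diary data. A few lines later it describes what the rule is for: "This approach to missing ePRO diary data assumed that the rate of migraine headache per day is the same for days with missing and nonmissing" diary days. Months with diary compliance of 50% or less are set to missing. The section carries the same adjustment to the other diary measures that need a 30-day basis, among them migraine days with acute medication use, a key secondary endpoint. The responder rates are computed from the adjusted counts.

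Three other places bear on the rule:

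- The opening of 5.4.1 normalizes without any condition: "Each month is defined as a 30-day period with migraine or headache measures normalized from the visit intervals".
- The normality sensitivity analysis in SAP 5.5.10.2 takes as its contrast the "total number of migraine headache days for each interval without normalization to 30-day period", and uses the log of compliant days over 30 as offset, again without a condition on period length.
- SAP 5.5.1.2 refers back to 5.4.1 for missing diary days, except for migraine attacks, where missing days are filled by carrying the last observation forward.

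**The concern.** The factor and its trigger address different things. The factor 30/x repairs missing entries; the trigger asks whether the period is 30 days long. The two agree except where the period is exactly 30 days and some entries are missing. There the SAP gives no instruction to scale, so the raw count stands, and a raw count over 30 days treats each missed day as free of migraine. That is the opposite of the equal-rate assumption stated in the same section.

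This is the derivation of the primary measure, and it also feeds the 50% and 75% response rates. The exempted length is also the planned one: the target intervals in the Schedule of Activities (Protocol Appendix 2) are 14 + 16, 30 and 30 days. Two competent programmers could build different primary datasets from the same text.

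**Working it through.** The plan gives no figure for this rule, so there is none to reproduce. The check compares the two readings.

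**1. The two rules.** Let L be period length, x the days with diary data and m the observed migraine days.

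- As written: m if L = 30, otherwise m × 30/x.
- As the stated assumption requires: m × 30/x in every period.

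They differ only when L = 30 and x < 30. The written rule then gives x/30 of the scaled value, a shortfall of 1 − x/30: 10% at x = 27, 20% at x = 24, 33.3% at x = 20.

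Example: m = 12, x = 24, L = 30. As written 12.0; scaled 12 × 30/24 = 15.0.

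**2. Responder status.** Take a complete baseline of 20 and a 30-day month with 6 missed days. A true count of 12 is a fall of 1 − 12/20 = 40%. The expected observed count is 12 × 24/30 = 9.6, recorded as a fall of 1 − 9.6/20 = 52%. The smallest true fall recorded as 50% is 1 − (10 × 30/24)/20 = 37.5%.

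**3. The cap.** A usable 30-day month needs more than 50% compliance, so at least 16 diary days. The largest shortfall is 1 − 16/30 = 46.7%. With a complete baseline, no true change and equal daily rates, missed days alone therefore cannot reach a 50% fall. The 100% rate cannot change at all, because scaling leaves zero at zero.

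**4. Baseline.** Protocol Appendix 2 sets a minimum of 30 days and inclusion criterion 7 asks for at least 80% of entries, so up to 6 of 30 days may be missed. If such a baseline is left unscaled, a true 20 is recorded as 20 × 24/30 = 16, and a complete month of 10 (a true 50% fall) is recorded as 1 − 10/16 = 37.5%. The error then runs the other way and hides a responder.

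**5. How often L = 30.** SAP 5.4.1 does not say how treatment-phase days are counted.

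- By simple date difference, every on-target month is 30 days and is exempt from scaling.
- By the count in SAP 5.5.7 (end date minus start date plus 1), an on-target month is 31 days and is scaled; a date difference of 29 gives L = 30. If that count is carried to baseline, a minimum-length baseline is 31 days and none is affected.
- If visits are spread evenly over their allowances (an assumption), Month 1 (14 ± 1 plus 16 ± 3 days) has L = 30 in 3 of 21 combinations, or 14%, and Months 2 and 3 (30 ± 2 days) in 1 of 5, or 20%. The shares are the same under either count.

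**6. Effect on the treatment difference.** The documents give neither missed-day frequency nor compliance by arm, so this is illustration only. Assume a true difference D = −2.0, equal compliance c in all arms, missingness unrelated to migraine, baseline unaffected, and a share f of months affected. The recorded difference is D × [1 − f(1 − c)].

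| f | c = 0.90 | c = 0.80 |
|---|---|---|
| 1/7 | −1.97 | −1.94 |
| 1/5 | −1.96 | −1.92 |
| 1 (all on target, simple date difference) | −1.80 | −1.60 |

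**The case against.** The strongest reply is that the SAP itself refutes the literal reading. It states the equal-rate assumption, normalizes unconditionally at the head of 5.4.1, and uses compliant days in the sensitivity offset. A programmer who follows the stated assumption would scale every period. The only count the SAP defines for injection intervals adds one day, so on-target months would be scaled anyway. Any attenuation under equal compliance is conservative. All of this stands as to intent and severity. It does not remove the defect: none of these passages overrides an explicit condition, the added-day count is defined for compliance and not for this trigger, and under that count a 29-day date difference still falls into the exempt case.

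A reader might infer more than the documents support:

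- *That the rule biases the trial in favour of the drug.* This would need missed days, or exactly 30-day periods, to differ between arms. The documents give no such figure.
- *That missed days turn unchanged patients into 50% responders.* The 46.7% cap rules this out under the conditions in step 3. The false responder in step 2 needs a true 40% fall as well as 6 missed days in an exactly 30-day month.
- *That moving a visit by one day changes the value for the same diary data.* A later visit adds a diary day. The jump from 12.0 to 15.0 occurs only if that day is missed too, giving 24 diary days out of 31.

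**Conclusion.** The rule is wrong as written; severity is minor. The inconsistency is certain from the text, and so is the error in an affected period: the count is too low by the fraction of days missed, up to 46.7%. The frequency is not known, because it turns on an unstated day count and on missed-day rates that the documents do not give. The effect on the treatment comparison is therefore unknown as well. Under the assumptions in step 6, an assumed difference of −2.0 becomes about −1.97 to −1.92 if 14% to 20% of months are affected, and −1.8 to −1.6 if all are. The movement is toward zero, and no between-arm bias is shown. The reason to act is that this is the primary-measure derivation and the correction is simple.

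**What to change.** Before Interim Analysis #2, which is the final analysis of the primary endpoint:

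1. Delete the condition on period length. Suggested wording: diary day and hour counts in every baseline and postbaseline period with compliance above 50% are multiplied by 30/x, where x is the number of days with diary data.
2. Keep the existing carry-forward of missing days for migraine attacks in SAP 5.5.1.2. Restricting the new sentence to day and hour counts avoids correcting attacks twice for the same missed days.
3. State one day-count convention for treatment-phase periods, consistent with SAP 5.5.7 or explicitly different from it.

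The cost is a few lines of SAP text and a check that the derivation program agrees. No new data are needed, and the primary model and multiple-testing procedure do not change.
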